1.5.3 Study Design Rationale

This Phase IIb study is a randomised, double-blind, placebo-controlled study of 365 days duration (plus screening and safety follow-up) that will be conducted to assess the efficacy and safety of monotherapy SC KY1005 in approximately 350 adult patients with moderate-to-severe AD. Sites will be selected globally to participate in this study. A parallel group design will be employed due to the testing of up to 4 different dose regimens versus Placebo. This is considered appropriate for a study of this type (EMEA/CHMP/SWP/28367/07 [Rev. 1] and ICH E4).

The study design, including the washout period and the use of Placebo, is in keeping with other trials in moderate-to-severe AD. The study is designed to assess monotherapy KY1005 in patients with limited treatment options. All patients therefore must have either had an inadequate response to topical therapies or be individuals for whom such topical treatment is inadvisable. It is recognised, based on prior studies in AD with a similar design [Thaçi The Lancet 2016], that the dropout rate can be relatively high (~20%) and this has been factored into the anticipated numbers of patients that will be recruited.

Although the study represents the initial clinical evaluation of SC KY1005, the enrolment of up to 350 patients in a Phase IIb study is considered to be acceptable due to the available clinical data for IV KY1005 in which no KY1005-specific risks have been identified. Furthermore, the non-clinical and clinical data for SC KY1005 have identified no KY1005-specific risks or local toxicity at the injection sites at clinically relevant doses.

The primary objective of this study will be to compare the dose response of 4 different dose regimens of KY1005 in patients with AD versus Placebo to Day 113 (Week 16). As part of the study design, patients initially enrolled at Baseline into the Placebo, 62.5 mg,125 mg and 250 mg KY1005 treatment arms who do **not** achieve ≥ EASI 75 or IGA 0/1 at Day 169 (Week 24) will have the opportunity to be to receive KY1005 from Day 169 (Week 24) by enrolling in an LTE study. This will enable all enrolled patients to have an opportunity to receive treatment at doses expected to elicit a meaningful clinical response (based on what was observed in the Phase 2a KY1005-CT02 study).

Patients who achieve \geq EASI 75 or who attain IGA 0/1 at Day 169 (Week 24) be randomised 3:1 to either enter a maintenance withdrawal phase or continue their pre-Week 24 dose/interval. The purpose being to characterise the durability of response in conjunction with PK following treatment discontinuation in those withdrawn from therapy and to assess the clinical response in those continuing to receive Q4W treatment at their pre-Week 24 dose. Those patients who are randomised to the second study period who subsequently lose clinical response will be offered the opportunity to receive retreatment with KY1005 in the LTE study. Results from this randomised withdrawal maintenance phase will inform the subsequent later stage development of KY1005 in the treatment of AD.

The maximum length of the study is 365 days plus safety follow-up. Those patients who achieve ≥ EASI 75 or who attain IGA 0/1 at Day 169 (Week 24) and complete the second study period without loss of clinical response at Day 365 (Week 52) will have an additional 112-day safety follow-up after Day 365 (Week 52) (total of 140 days safety follow-up from receipt of last dose of IMP on Day 337 [Week 48]). If during safety follow-up or after the end of study this cohort of patients experience worsening of their AD, and in the investigator's opinion re-treatment with KY1005 is considered appropriate, they may be considered for enrolment in the LTE (subject to meeting inclusion/exclusion criteria).

1.5.4 Study Setting

The Sponsor plans to conduct the study at selected global sites.

All study procedures will be conducted by trained Investigators and medical staff with appropriate levels of training, including Good Clinical Practice (GCP) and experience of clinical trials. Investigators must understand specific characteristics of the IMP and of its target and mode of action. This information can be found within this protocol and within the IB.

Unless Appendix 14 (Section 17.14) is activated, IMP administration must take place in appropriate clinical facilities, under controlled conditions with the possibility of close

supervision of study patients during and after dosing, as required by the protocol. Units must have immediate access to equipment and appropriately qualified staff for resuscitating and stabilising individuals in an acute emergency (such as cardiac emergencies, anaphylaxis, cytokine release syndrome, convulsions, hypotension), and ready availability of intensive care unit and other hospital facilities.

1-Mar-2022

Version number: 1

1.6 Summary of Known and Potential Risks and Benefits

Clinical and non-clinical studies confirm that KY1005 exerts the intended pharmacological effect in relevant immune systems, and can provide meaningful clinical improvement in the signs and symptoms of AD. The benefits of KY1005 in moderate-to-severe AD have been demonstrated in the KY1005-CT02 Phase 2a study where both KY1005 treatment groups provided clinically meaningful improvements in the signs and symptoms of disease.

KY1005-specific risks, including none associated with SC administration, have not been identified to date from the non-clinical or clinical programme. Potential risks include malignancy and impaired response to infection (discussed

tested to date. One patient in the prior healthy volunteer study (KY1005-CT01) experienced a reaction of the mouth and throat during systemic administration on first exposure to KY1005. No similar events were noted in the KY1005-CT02 Phase 2a study in AD patients nor the KY1005-CT04 SC healthy volunteer study. Systemic or localised allergic reactions that require immediate treatment are therefore defined as an adverse event of special interest (AESI; see Section 8.1.3) so that specific information can be collected prospectively.

Overall, to date blockade of OX40/OX40L in humans is precedented without acute severe adverse consequences. These findings suggest that OX40L-mediated clearance is not relevant at pharmacological doses and that such binding, in disease states in which OX40L is

upregulated, does not lead to common adverse reactions. Mitigation of the theoretical risks is possible through selection of appropriate study populations and monitoring in clinical trials. The overall benefit risk is therefore in favour of continued development of KY1005 in immune mediated disease such as AD.

Further details can be found in the IB.

1.6.1 Benefit/Risk of KY1005 Regarding Potential Infections with Severe Acute Respiratory Syndrome Coronavirus 2 (SARS-Cov-2)

There is no change in the overall benefit/risk of treating patients with KY1005 regarding the Coronavirus Disease 2019 (COVID-19) pandemic. In case of the implementation of restrictions due to COVID-19, the advice provided in Section 17.14 (Appendix 14) should be followed.

1.7 Route of Administration, Dosage, Dosage Regimen and Treatment Period(s)

KY1005 will be administered by SC injection. Each dose will be administered as described in the Pharmacy manual (Section 5.2). Following completion of the SC injection, patients will be monitored for at least 60 minutes.

Patients will receive treatment with KY1005 or matching Placebo every 28 days throughout the study. Those patients randomised to withdrawal post-Week 24 will be administered Placebo every Q4W when KY1005 is not received. This is to maintain the blinding of the study.

The dosing schedule is presented in Table 1-3.

Table 1-3 DosingSchedule

	Baseline**		Randomised Withdrawal Period From Day 169 (Week 24) to Day 365 (Week 52)
Treatment regime	Dose IMP (SC)	Dose IMP (SC)	Dose IMP (SC)
Group 1	500 mg	250mg Q4W	Withdrawal: Placebo 0 mg Q4W
			Pre-Week 24: 250 mg Q4W
Group 2	PBO and	250 mg Q4W	Withdrawal: Placebo 0 mg Q4W
	(0 mg)*		Pre-Week 24: 250 mg Q4W
Group 3	125 mg and PBO	125 mg Q4W	Withdrawal: Placebo 0 mg Q4W
	(0 mg)*		Pre-Week 24: 125 mg Q4W
Group 4	62.5 mg and	62.5 mg Q4W	Withdrawal: Placebo 0 mg Q4W
	PBO (0 mg)*		Pre-Week 24: 62.5 mg Q4W
Placebo	PBO (0 mg)*	0 mg Q4W	Withdrawal: Placebo 0 mg Q4W
			Pre-Week 24: 0 mg Q4W

IMP=investigational medicinal product; PBO=placebo; Q4W= every 4 weeks; SC=subcutaneous.

^{*} Placebo will be administered as a second SC injection at Baseline to maintain the blind.

2 OBJECTIVES AND ENDPOINTS

2.1 Study Objectives

2.1.1 Primary Objective and Endpoint

Objective	Endpoint
To characterise the efficacy (including dose/exposure-response) across a range of KY1005 exposures compared to Placebo on the signs of AD using the Eczema Area and Severity Index (EASI) in those patients who have who have a documented history, within 6 months prior to Baseline, of either inadequate response to topical treatments or inadvisability of topical treatments.	Percentage change in EASI from Baseline to Day 113 (Week 16).

1-Mar-2022

Version number: 1

2.1.2 Secondary Objectives and Endpoints

[figure not shown]
Objectives	Endpoints
Safety and tolerability of KY1005.	Incidence of treatment-emergent adverse events.
The pharmacokinetic profile across a range of KY1005 doses/exposures.	Serum KY1005 concentration assessed throughout the study.
The response across a range of KY1005 exposures on additional physician assessment-s of atopic dermatitis (AD) activity/severity (EASI 50, EASI 75, EASI 90, EASI 100, Investigator Global Assessment [IGA], SCORing of Atopic Dermatitis [SCORAD] Index and affected body surface area [BSA]).	 Key secondary endpoints: Percentage change from Baseline in EASI at Day 169 (Week 24). Percentage of patients with at least a 75% reduction from Baseline in EASI (EASI 75) at Days 113 (Week 16) and 169 (Week 24). Percentage of patients with a response of IGA 0 or 1 and a reduction from Baseline of ≥2 points at Days 113 (Week 16) and 169 (Week 24). Proportion of patients with improvement (reduction) of weekly average of pruritus NRS ≥4 with a Baseline pruritis NRS of ≥4 from Baseline to Days 113 (Week 16) and 169 (Week 24). Other secondary endpoints: Absolute change from Baseline in EASI at Days 15 (Week 2), 29 (Week 4), 57 (Week 8), 85 (Week 12), 113 (Week 16), 141 (Week 20) and 169 (Week 24). Percentage change from Baseline in EASI at Days 15 (Week 2), 29 (Week 4), 57 (Week 8), 85 (Week 12) and 141 (Week 20). Percentage of patients with at least a 50% reduction from Baseline in EASI (EASI 50) at Days 15 (Week 2), 29 (Week 4), 57 (Week 8), 85 (Week 12), 113 (Week 16), 141 (Week 20) and 169 (Week 24). Percentage of patients with at least a 75% reduction from Baseline in EASI (EASI 75) at Days 15 (Week 2), 29 (Week 4), 57 (Week 8), 85 (Week 12), and 141 (Week 20).

Objectives	Endpoints
	• Percentage of patients with at least a 90% reduction from Baseline in EASI (EASI 90) at Days 15 (Week 2), 29 (Week 4), 57 (Week 8), 85 (Week 12), 113 (Week 16), 141 (Week 20) and 169 (Week 24).
	• Percentage of patients with at least a 100% reduction from Baseline in EASI (EASI 100) at Days 15 (Week 2), 29 (Week 4), 57 (Week 8), 85 (Week 12), 113 (Week 16), 141 (Week 20) and 169 (Week 24).
	• Change in IGA from Baseline to Day 169 (Week 24) and over time.
	• Percentage of patients with a response of IGA 0 or 1 and a reduction from Baseline of ≥2 points at Days 15 (Week 4), 29 (Week 4), 57 (Week 8), 85 (Week 12), and 141 (Week 20).
	• Absolute and Percentage in SCORAD Index from Baseline to Day 169 (Week 24) and over time.
	Absolute and Percentage change in affected BSA from Baseline to Day 169 (Week 24) and over time.
The response across a range of KY1005 dose/exposures on patient reported AD activity/severity (Atopic dermatitis Control Tool [ADCT], Patient Oriented [PO] Eczema Measure [POEM], Dermatology Quality of Life Index [DLQI], Hospital Anxiety and Depression Scale [HADS], and Numerical Rating Scale [NRS] for pruritus).	 Absolute and Percentage change in POEM from Baseline to Day 169 (Week 24) and over time. Absolute and Percentage change in DLQI from Baseline to Day 169 (Week 24) and over time. Absolute and Percentage change in ADCT from Baseline to Day 169 (Week 24) and over time. Absolute and Percentage change in HADS from Baseline to Day 169 (Week 24) and over time. Absolute and Percentage change in weekly average of pruritus NRS from Baseline to Day 169 (Week 24) and over time. Proportion of patients with improvement (reduction) of weekly average of pruritus NRS ≥3 with a Baseline pruritis NRS of ≥3 from Baseline to Days 113 (Week 16) and 169 (Week 24).
The pharmacodynamic response to KY1005 including but not limited to: The immunogenicity of KY1005, including the anti-KY1005 antibody response.	The immunogenicity of KY1005, including the anti-KY1005 antibody response.
The explore the continued clinical response in those patients who achieve ≥ EASI 75 or who	Continued assessment of the efficacy endpoints from Day 169 (Week 24) and over time.
attain IGA 0/1 at Day 169 (Week 24)	Time to loss of EASI 75 in participants randomised to withdrawal post-Week 24.
	• Time to loss of IGA 0/1 in participants randomised to withdrawal post-Week 24.
	• Time to loss of EASI 50 in participants randomised to withdrawal post-Week 24.
	• Continued assessment of patient reported AD activity/severity endpoints from Day 169 (Week 24) and over time.

1-Mar-2022

Version number: 1

2.1.3 Exploratory Objectives and Endpoints

3 STUDY DESIGN

3.1 Overall Study Design and Plan

This is a Phase IIb, randomised, double-blind, placebo-controlled, parallel group, multicentre dose ranging study to characterise the efficacy and safety of SC administered KY1005 in adult patients with moderate-to-severe AD who have a documented history, within 6 months prior to Baseline, of an inadequate response to, or inadvisability of, topical treatments.

Up to 350 patients (approximately 70 patients per treatment arm) will be enrolled. Patients who continue to meet the eligibility criteria at Baseline will be randomised to 1 of 5 treatment groups (4 different KY1005 regimens or Placebo) in an equal (1:1:1:1) ratio.

From Baseline up to Day 169 (Week 24) IMP will be administered at the following dose and intervals:

- 500 mg loading at baseline () followed 4 weeks later with 250 mg Q4W as ;
 - 250 mg at Baseline followed 4 weeks later with 250 mg Q4W ;
- Or
 125 mg (at Baseline followed 4 weeks later with 125 mg Q4W as ;
- Or

 62.5 mg (at Baseline followed 4 weeks later with 62.5 mg Q4W as ;
 Or

Property of the Sanofi Group - strictly confidential

•	Placebo given as	at Baseline followed 4 weeks later with	
	Placebo (0 mg).		

1-Mar-2022

[figure not shown]
Version number: 1

At Baseline, those patients not receiving a KY1005 loading dose will receive both KY1005 and Placebo to maintain the study blind.

The Day 113 (Week 16) primary analysis will occur once all patients have reached the Day 169 (Week 24) visit (or earlier in the event of termination).

To enable Placebo patients and those patients randomised to the KY1005 62.5 mg Q4W, 125 mg and 250mg Q4W treatment arms to receive KY1005 at a dose expected to elicit a meaningful clinical response (based on prior clinical evidence), patients who do **not** achieve ≥ EASI 75 or IGA 0/1 at Day 169 (Week 24) will be invited to enrol in the LTE study where they will receive KY1005.

In those patients who achieve ≥ EASI 75 or who attain IGA 0/1 at Day 169 (Week 24), a randomisation will occur pre-dose at Day 169 (Week 24) and patients will enter the second study period. This will occur irrespective of whichever dose group the patient was randomised to at Baseline including Placebo. Patients will be randomised in a 3:1 manner to be withdrawn from therapy or to continue their pre-Week 24 dose/interval. To maintain the blind, those patients randomised to the Withdrawal arm will receive Placebo Q4W. Those patients who are re-randomised at Day 169 (Week 24) who lose their clinical response will be offered the opportunity to be retreated with KY1005 in the LTE study. Loss of clinical response is defined as the first instance of <EASI 50 during the second study period and where rescue therapy is no longer permitted as per Section 5.3.4. If loss of clinical response from Day 197 (Week 28) occurs, Investigators will be able to choose to discontinue the patient from KY1005-CT05

At Day 365 (Week 52), patients who have completed the post-Week 24 period and have not experienced loss of clinical response will have an additional 112 days' safety follow-up up to Day 477 (Week 68) and then be discharged from the study. The last dose will be given no later than Day 337 (Week 48) and as such safety follow-up will be 140 days following last dose of IMP. If during safety follow-up or after the end of study this cohort of patient's experience worsening of their AD, and in the investigator's opinion re-treatment with KY1005 is considered appropriate, they may be considered for enrolment in the LTE (subject to meeting inclusion/exclusion criteria).

The overall study design is presented in Figure 3-1.

3.2 Study Duration

The duration of the study will be up to 28 days for screening and then up to approximately Day 477 (Week 68) (to Day 365 [Week 52] plus 112 days safety follow-up,

for all

[figure not shown]
patients unless enrolled into the LTE study at Day 169 (Week 24) or due to loss of clinical response at or after Day 197 (Week 28). The last dose will be given no later than Day 337 (Week 48).

3.2.1 Study flow

The overall study design is presented in Figure 3-1.

1-Mar-2022 Version number: 1

Figure 3-1: Overall StudyDesign

AD=atopic dermatitis; IMP=investigational medicinal product; EP=endpoint; EASI=eczema area and severity index; IGA= investigator global assessment; LTE=long-term extension; Q4W=every 4 weeks; NA=not applicable.

- a On Day 169 (Week 24), patients are re-randomised prior to IMP administration on the basis of their Day 169 (Week 24) response.
- Patients initially enrolled at Baseline into the Placebo, 62.5 mg, 125 mg and 250 mg KY1005 treatment arms who do not achieve ≥ EASI 75 or IGA0/1 at Day 169 (Week 24) will have the opportunity to receive KY1005 Q4W from Day 169 (Week 24) by enrolling in a long-term extension (LTE) study (LTS17367 LTE). Participation in the LTE is subject to meeting the inclusion/exclusion criteria. Any patient who in the Investigator's opinion should not be enrolled into the LTE, or where the patient declines further participation will have an additional 112 days safety follow-up from Day 141 (Week 20) and then be discharged from the study.
- c Patients who achieve ≥ £ASI 75 or who attain IGA0/1 at Day 169 (Week 24), irrespective of their Baseline group will be randomised 3:1 to either enter a maintenance withdrawal phase or continue on their pre-Week 24 dose/interval.

- d If loss of response from Day 197 (Week 28) occurs between visits and retreatment with KY1005 is considered appropriate, patients will be permitted to move to the LTE (subject to meeting the inclusion/exclusion criteria for the LTE). Loss of clinical response is defined as < EASI 50 during the second study period and where rescue therapy is no longer permitted as per Section 5.3.4. Patients who in the Investigator's opinion should not be enrolled into the LTE, or where the patient declines further participation, will enter safety follow-up.
- e Patients who are responders at Day 169 (Week 24) and complete the second study period to Day 365 (Week 52) without loss of clinical response will enter safety follow-up. If during safety follow-up or after end of study the patients experience worsening of their AD, and in the investigator's opinion re-treatment with KY1005 is considered appropriate, they may be considered for enrolment in the LTE (subject to meeting inclusion/exclusion criteria).

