3.4 Definition of End of Study

The EOS is defined as the last patient undergoing the last visit of the study. This will either be:

• Day 169 (Week 24) (or earlier termination) for those patients who do **not** achieve ≥ EASI 75 or IGA 0/1 at Day 169 (Week 24), and are subsequently enrolled in the LTE;

Or

• Day 281 (Week 40) (or earlier termination) for those patients who do **not** achieve ≥ EASI 75 or IGA 0/1 at Day 169 (Week 24), and are **not** enrolled in the LTE and have additional safety follow-up to a total of 140 days after the last dose of IMP;

Or

Day 365 (Week 52) (or earlier termination) for those patients who achieve ≥ EASI 75 or who attain IGA 0/1 at Day 169 (Week 24) and continue on either their pre-Week 24 dose/interval or enter the withdrawal arm, experience loss of clinical response at or after Day 197 (Week 28) and are enrolled in the LTE. Those patients not enrolled in the LTE will have additional safety follow-up to a total of 140 days after the last dose of IMP;

Or

• Day 477 (Week 68) (or earlier termination) for those patients who reach Day 365 (Week 52), are still considered to be responding to study treatment, and are **not** enrolled in the LTE and have additional safety follow-up to a total of 140 days after the last dose of IMP.

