3.5 Early Study Termination

The study can be terminated at any time for any reason by the Sponsor (including approval or the favourable opinion is revoked, in the event of a negative change in the benefit/risk ratio when the necessary adjustment to the maximum sum insured is not possible; failure to enrol; futility; safety decision etc). If the trial is suspended or terminated early, the Investigator will promptly inform the trial patients and should assure appropriate therapy and follow-up.

No further IMP will be given to a patient if any study permanent discontinuation rules are met (see Section 9.1), including recommendation of the Independent Data Monitoring Committee (IDMC; Section 3.8). If a patient withdraws from the study treatment early but consent is retained, study assessments may be continued until a) Day 169 (Week 24) for patients who withdraw from study treatment during the first study period and therefore are **not** eligible for

Version number: 1

1-Mar-2022

LTE, or b) until Day 365 (Week 52) or the end of the safety follow-up period in patients who withdraw from study treatment after Day 169 (Week 24).

Unless patients continue in the LTE at Day 169 (Week 24) or due to loss of clinical response at or after Day 197 (Week 28), a safety follow-up for 140 days after the last dose of IMP will be required.

In addition, the Investigator may withhold further IMP from a patient if they report moderate-or-severe (regardless of seriousness) adverse reactions which are attributed to the IMP. There will be no obligation to unblind treatment allocation in making this decision.

The Sponsor may discontinue the entire study at any time based on information received during the running of the study that demonstrates an unexpected risk or absence of benefit to patients. This may for example follow the request of the IDMC or where additional information emerges either during the study or from other sources (eg, literature or Health Authorities).

If the study is discontinued, where patients withdraw early or where IMP has been discontinued by the Investigator, patients will be required to be followed-up for a minimum of 140 days for safety evaluation.

Further details of IMP discontinuation are provided in Section 9.1.

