6.4.3 Adverse Events

Investigators must carefully monitor patients for the occurrence of AEs, including clinical laboratory, vital signs and ECG variables. Assessments must be made of the seriousness, severity and relationship to the administration of study treatment (causality). Serious adverse events and specific AESI will require expedited reporting to the Sponsor. For details on definitions and reporting procedures see Section 8.1.

Adverse event assessments must be made by the Investigator or delegated to an appropriately trained and experienced physician. The Investigator is required to record the assessments in the eCRF and patient's medical notes. Any AEs already recorded and designated as "continuing" should be reviewed at each subsequent assessment.

During and following a patient's participation in this study, the Investigator must ensure that adequate medical care is provided to a patient for any AEs, including clinically significant laboratory values, related to the trial.

Adverse events and SAEs will be collected from the time of the patient signing the ICF until completion of the last visit. If an event that starts after the safety follow-up period is due to a late onset toxicity to study treatment, then it should be reported as an AE or SAE as applicable.

Investigators are not obligated to actively seek AE or SAE in former study patients. However, if the Investigator learns of any SAE, including a death, at any time after a patient's last visit and he/she considers the event to be reasonably related to the study treatment or study participation, the Sponsor should be notified.

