8 SAFETY MONITORING AND REPORTING

8.1 Definition of an Adverse Event

The ICH E6(R2) Good Clinical Practice Guideline defines an AE as any untoward medical occurrence in a patient or clinical investigation patient administered a pharmaceutical product, which does not necessarily have to have a causal relationship with this treatment. An AE can, therefore, be any unfavourable and unintended sign (including an abnormal laboratory finding), symptom or disease temporally associated with the use of a medicinal (investigational) product, whether or not considered related to the medicinal (investigational) product.

An AE can include an undesirable medical condition occurring at any time, even if no investigational medicinal product has been administered. This includes an exacerbation of pre-existing conditions or events, intercurrent illnesses, drug interaction, or the significant worsening of the indication under investigation that is not recorded elsewhere on the eCRF under specific efficacy assessments. Anticipated fluctuations of pre-existing conditions, including the disease under study, that do not represent a clinically significant exacerbation or worsening are not considered AEs and will not be captured as AEs. Lack of efficacy or failure of expected pharmaceutical action per se will not be reported as an AE or a SAE. Such instances will be captured under the efficacy assessments. However, the signs symptoms and clinical sequelae resulting from lack of efficacy will be reported as an AE/SAE if they fulfil the definition of an AE or SAE.

This definition includes events occurring from the time of the patient giving informed consent until the 140 days after the last dose of IMP.

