10.4.2.4.1 Adverse Events

The primary safety endpoint is the incidence of TEAEs.

All AEs in the clinical trial database will be coded according to MedDRA, which will be used to summarise AEs by primary System Organ Class (SOC) and Preferred Term (PT). All AEs will be displayed in listings.

A TEAE is defined as an AE observed starting after the first administration of IMP up until 140 days after the last IMP administration. All TEAEs collected during the main study (to Day 169 [Week 24]) will be summarised. Additionally, all TEAEs collected during the second study period in those patients who achieve ≥ EASI 75 or who attain IGA 0/1 response following 24 weeks of treatment will be summarised (to Day 365 [Week 52]).

Version number: 1

1-Mar-2022

The number and percentage of patients with TEAEs and the number of TEAEs will be summarised in each KY1005 treatment regimen and in the Placebo group.

The number and percentage of patients with TEAEs/AESIs will be further tabulated by causality and severity (mild, moderate and severe) in each KY1005 treatment regime and in the Placebo group.

In addition, the number and percentage of patients with SAEs, TEAEs leading to treatment discontinuation, TEAEs leading to study discontinuation and AEs leading to death will be summarised in each KY1005 treatment regimen and in the Placebo group.

Adverse events will be listed by treatment allocation, grouped by primary SOC and sub-grouped by PT and causality.

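### Figure 3-1 footnote b ends safety follow-up for Week 24 non-responders outside the LTE on Day 253, 28 days before the Day 281 end that Section 3.4 sets for them

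*Protocol*

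**What the plan says.** **The footnote.** Protocol Section 3.2.1, Figure 3-1 footnote b, covers patients who do not respond at Week 24 and do not go into the LTE, by the investigator's judgement or their own choice. They "will have an additional 112 days safety follow-up from Day 141 (Week 20") and are then discharged.

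**The rest of the protocol.** Section 3.4 sets the end of study at "Day 281 (Week 40) (or earlier termination) for those patients who do" not respond at Week 24 and stay outside the LTE, and says that they "have additional safety follow-up to a total of 140 days after the last dose of IMP". Section 3.5 states that, unless the patient continues in the LTE, "a safety follow-up for 140 days after the last dose of IMP will be required". The adverse event definition in Section 8.1 covers events "from the time of the patient giving informed consent until the 140 days after the last dose of IMP". Section 10.4.2.4.1 counts an event as treatment-emergent "up until 140 days after the last IMP administration".

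**The visit schedule.** Section 6.1 and Table 6-4 footnote a assign Table 6-4 to patients outside the LTE who need follow-up. The table prints Days 393, 421 (telephone), 449 and 477. Section 6.4.4 places the follow-up pregnancy tests on Days 393, 449 and 477.

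**The concern.** The footnote and Section 3.4 give different discharge dates for the same patients, and the footnote falls short of the 140-day rule. This affects data collection because of Section 6.4.3: "Adverse events and SAEs will be collected from the time of the patient signing the ICF until completion of the last visit", and "Investigators are not obligated to actively seek AE or SAE in former study patients". If the last visit comes too early, routine collection stops with it, while the treatment-emergent window stays open. Events in the gap would be missing from the database without being recorded as missing.

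The schedule adds a smaller difficulty. A site that turns to Table 6-4 for a patient leaving at Week 24 finds no printed day before Day 393, which is after that patient's study has ended.

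**Working it through.** **Inputs.** Follow-up of 112 days counted from Day 141 (footnote b). End of study on Day 281 and follow-up of 140 days after last dose (Section 3.4). Last dose on Day 337 for patients who complete the second period, with 112 days counted from Day 365 (Sections 1.5.3 and 3.1). Printed follow-up days 393, 421, 449 and 477, each with a window of ±7 days (Table 6-4). Weeks are (day − 1)/7.

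**1. Reproduce Section 3.4.** The implied last dose is 281 − 140 = Day 141. Going forward, 141 + 140 = Day 281, and (281 − 1)/7 = Week 40, as printed. Counting from the Week 24 visit gives the same day: 169 + 112 = 281.

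**2. Check the responder path.** 337 + 140 = 477 and 365 + 112 = 477 (Week 68). So 112 days is the right length when the count starts at the visit 28 days after the last dose.

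**3. Footnote b.** 141 + 112 = Day 253, and (253 − 1)/7 = Week 36. It appears to pair the 112-day length with the dosing day instead of the visit 28 days later.

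**4. Shortfall.** 281 − 253 = 28 days, and 28/140 = 20%. A ±7-day visit window does not cover this.

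**5. Table 6-4.** Offsets from Day 337 are 393 − 337 = 56, 421 − 337 = 84, 449 − 337 = 112 and 477 − 337 = 140. The printed days therefore fit a Day 337 last dose only. For a Week 24 exit, none of the four falls within Days 169 to 281, and the earliest comes 393 − 281 = 112 days after the end of study.

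**6. The same offsets from Day 141.** 141 + 56 = 197, 141 + 84 = 225, 141 + 112 = 253 and 141 + 140 = 281. The last agrees with Section 3.4. On this schedule the footnote drops one contact of four. Table 6-4 marks Visits 31 and 32 alike for examination, vital signs, ECG, laboratory and pregnancy tests, so each of these would still be done on Day 253.

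**7. Which summary Days 253 to 281 reach.**

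| Place | Period covered | Counts Days 253–281 for a patient who completed Week 24? |
|---|---|---|
| Protocol 10.4.2.4.1, main-study TEAE summary | to Day 169 | No |
| SAP 9.1, Treatment Period 1 summary | to the Week 24 visit; extended to last dose + 140 days only after early treatment discontinuation | No, as worded |
| SAP 9.1, overall TEAE summary | first dose to last dose + 140 days | Yes |
| SAP 4.4.1, Part 1 non-efficacy data | to end of study involvement if the patient does not enter Part 2 | Yes |

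**The case against.** The best defence is that this is one wrong anchor in a figure footnote. Sections 3.4, 3.5, 8.1 and 10.4.2.4.1 all use 140 days, and Section 3.4 names Day 281 for exactly these patients. That is true and lowers the risk, but the footnote is a discharge instruction in its own right and remains wrong.

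Three stronger readings are tempting, and the documents do not support them.

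- **That the primary safety comparison is compromised.** TEAE incidence is the primary safety endpoint, so a reader might infer this. For a patient who completed Week 24, the main-study summary and the SAP Period 1 table as worded stop before Day 253. Section 6.4.3 also keeps late-onset toxicity reportable as an AE or SAE after follow-up, and related SAEs reportable whenever the investigator learns of them. What is lost is mainly new events that nobody recognises as late-onset toxicity.
- **That the shortfall is larger because a dose was given on Day 169.** Section 5.2.5 describes injections running to Day 169, and Table 6-2 marks dosing on that day. But a Day 169 dose would put the end of follow-up at 169 + 140 = Day 309, contrary to Section 3.4. Day 281 and the footnote's own anchor both point to Day 141.
- **That sites have no usable dates and no rule for deriving them.** Section 3.4 fixes the final day, so only the interim dates are missing. Text beside the follow-up duration is blacked out in SAP Section 3.1, and there is a gap at the same place in protocol Section 3.2. One can say only that the visible text gives no conversion.

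**Conclusion.** Footnote b is wrong as written. It ends follow-up 28 days (20%) short of the 140 days that the protocol requires elsewhere. The conclusion rests on a Day 141 last dose, which is inferred from Section 3.4 and from the footnote's anchor and is not stated in a sentence. The practical effect is confined to Week 24 non-responders outside the LTE, whose number is not given, at sites that follow the footnote in preference to Section 3.4. In the analysis it would show chiefly in the overall TEAE summary.

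The mismatch in Table 6-4 and Section 6.4.4 is real but secondary. It should be corrected for clarity and does not remove the end date. Both points are worth correcting; neither threatens the trial's main conclusions.

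**What to change.** **Main change.** Reword footnote b to give 140 days of safety follow-up from the last dose on Day 141 (Week 20), that is, to Day 281 (Week 40). Giving 112 days from Day 169 (Week 24) is equivalent and matches the way the responder path is described.

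**Secondary change.** Label the Table 6-4 visits as last dose +56, +84 (telephone), +112 and +140 days. Label the Section 6.4.4 follow-up pregnancy tests as last dose +56, +112 and +140 days. Anchoring to the last dose also serves patients who stop treatment early and decline further visits, whom Section 9.1.3 sends to the same schedule.

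**Cost.** One footnote, one row of visit days and one sentence, with no follow-up beyond the 140 days already required. The small downside is that sites must calculate dates for each patient instead of reading fixed days.
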